9. COMPENSATION

Will participants be compensated for participation?

Participants will be compensated at the completion of each testing cycle or after the final visit to the lab.

If so, please include details.

Participants will receive this payment in the form of a check.

For each 14-day ambulatory assessment portion of the study (including daily saliva collection), there is a base compensation of \$200, with a \$50 bonus for the completion of both morning/evening surveys on ≥ 12 days. For example, if a participant finishes the 14-day protocol and completes both morning/evening surveys on 12 days total morning/evening surveys (out of 14 total), he/she will be compensated \$250. If a participant finishes the 14-day protocol and completes both morning/evening surveys on 10 days (out of 14 total), he/she will be compensated \$200. For each experimental laboratory visit, participants will be compensated \$100. If a participant completes all parts of a testing cycle, the maximum compensation is \$350.

If a participant completes all parts of both testing cycles, he/she will be compensated \$700 (as described above), plus an additional \$150 bonus. The maximum compensation for completion of the entire study is \$850. If, for example, a participant receives the maximum compensation, he/she will receive one check for \$350 after the first testing cycle and a second, separate, check for \$500 after the second testing cycle.

The Internal Revenue Service (IRS) considers all payments made to research subjects to be taxable income. Participant's personal information, including their name, address, and social security number, may be acquired provided to the University of Delaware's accounting office for the purpose of payment. If total payments for the year exceed \$600.00, the University of Delaware will report this information to the IRS as income and participants will receive a Form 1099 at the end of the year. If participants receive less than \$600.00 total for payments in a year, they are personally responsible for reporting the payments to the IRS.

10. DATA

Will subjects be anonymous to the researcher?

No

If subjects are identifiable, will their identities be kept confidential? (If yes, please specify how)

Yes

All files will be coded with a unique code for each subject. Documents allowing identification of participants do not leave the investigator's labs and are only available to authorized persons. The list linking participant names to their participant numbers (codebook) will be digitized and stored in REDCap, in a project separate from all de-identified data. Records across the REDCap projects are not linked, thus personal identifiable information is not associated with any data collected except for the linking codebook document. The data captured in Project 1 will contain personally identifiable information and include the IRB-approved consent, the pre-screening survey, subject contact information, and the compensation report form. Project 1 will also contain the list linking participant names to their participant numbers, which will be the only way to link the participant ID with their personal identifiable information. Project 2 will not contain personal identifiable information and will include all other coded data collected via survey, as well as all other coded data collected during the experimental visit. Any paper forms of data will be digitized and imported into REDCap. REDCap is a HIPAA compliant database. Only approved project staff will have access to the REDCap databases, which will only be accessed via secure connection (UD VPN).

Note: REDCap eConsent will be used to secure electronic signatures for adult participants,

parents, legal guardians, children, witnesses, and study personnel. The REDCap eConsent will contain identical information as a paper consent, and will have automatic archiving of signed consent documents with date and time stamps for audit purposes. PDF copies of the signed consent document can be generated to give to participants. Electronic consents will be stored in a file repository on the REDCap database system in a separate REDCap database not linked to any other REDCap databases or data.

Subjects may give permission to have their contact information retained in the investigator's secured files if they wish to be considered for participation in future studies. After the investigators complete the study, they remove all identifiers from the data and store the data indefinitely.

How will data be stored and kept secure (specify data storage plans for both paper and electronic files. For guidance see <http://www.udel.edu/research/preparing/datastorage.html>)

Hard (paper) copies of informed consents will be scanned and uploaded to REDCap; hard paper copies will be shredded.

Any paper files will be stored in a locked cabinet. These files are coded and do not contain personal identifying information. Only approved project staff will have access to the data.

All electronic data will be encrypted. All electronic data are coded and do not contain personal identifying information. The data will be stored using UD-sanctioned storage tools and archived for potential use in other, future studies. In the event of any publication or presentation resulting from the research, no personally identifiable information will be revealed. Only approved project staff will have access to the data.

Some data for this project will be stored in CHRC's REDCap instance, a highly secure and robust web-based research data collection and management system. REDCap is managed by CHRC's Data Systems Analysts ensuring fidelity of database configuration and back-ups. User activities are logged to enable auditing of all data changes. Each project must have a UD full time faculty member with the User Rights privileges and they are responsible for ensuring appropriate access/role to study data via the User Rights Module. REDCap employs a robust multi-level security system that enables researchers to easily implement "minimum necessary" data access for their research staff, including specification of data fields that are identifiers. This feature includes "single click" ability to provide completely deidentified (removing all identified data fields and shifting dates) for analysis or other purposes. All users are given individual user IDs and passwords and their access is restricted on a role-specific basis. Each user must be sponsored by a UD full time faculty member. User activities are logged to enable auditing of all data access.

Qualtrics will be accessed via The Pennsylvania State University institutional contract; associated data will be reduced and exported by our Co-Investigator [name]. Qualtrics is a secure website and survey application designed to support data capture for research studies. All web traffic to and from the Qualtrics application website is done via a Secure Socket Layer (SSL) that encrypts the data in transmission. The surveys contain statements advising of the limitations of the technology and that there is no confidentiality guarantee. Data are deleted from Qualtrics' servers within 24 hours after the user deletes it from the website. The cognitive function assessments administered via Gorilla experiment builder will not contain any identifiers; the link to access the Gorilla experiment builder (in Qualtrics) will include the unique identifier connecting the participant's Qualtrics survey results to their Gorilla task results. Data are removed from Gorilla's backup servers within 14 days of deletion.

Laboratory-provided smartphones are password protected and will only be used to capture de-

identified data streams. There will be no other identifying types of data captured.

Metricwire was built to protect the most sensitive research data and comply with the Health Insurance Portability and Accountability Act (HIPAA) and 21 CFR Part 11 (Electronic Signatures in Clinical Research) in the United States and the General Data Protection Regulation (GDPR) in the EU. The Metricwire mobile app is also FDA compliant. Data streams collected via the Metricwire mobile app are linked to a variable code that contains no identifying information. No identifiable information will be (or can be) entered into the Metricwire smartphone app, nor does the app collect any identifiable information from the smartphone. Data collected via the Metricwire mobile app are immediately synced to Metricwire cloud servers in the US via WiFi connection and/or mobile network and removed from the device. All data are encrypted end-to-end during transmission using TLS 1.3 Protocol, an updated and more secure version of SSL. If there is no network connection, data are temporarily stored on the mobile device until an online connection is re-established using AES-256 encryption. Temporarily stored data cannot be accessed using application interfaces. Metricwire servers use an Encryption Token to verify that the data are coming from the correct source (authenticity) and that data have not been modified in-transit (integrity). Data are stored without identifiers within the Metricwire platform/server until exported directly from the Metricwire server dashboard by the study team. The server is accessed via an encrypted website portal that is password protected and only accessible to study personnel. No data on the server will include participant identifiers.

How long will data be stored?

Upon study closure, all data will be de-identified and stored indefinitely in a locked cabinet or password protected computer. All data will be encrypted.

Will data be destroyed? YES NO (if yes, please specify how the data will be destroyed)

Screening data from subjects who are not accepted into the study are shredded immediately.

Will the data be shared with anyone outside of the research team? YES NO (if yes, please list the person(s), organization(s) and/or institution(s) and specify plans for secure data transfer)

How will data be analyzed and reported?

To ensure robust and unbiased results, we will use defined protocols for including/excluding, enrolling, and testing subjects. Multiple experimental controls and orthogonal approaches will be used, and relevant psychobiological variables are factored into the research design and analyses. Data analysis will be blinded, when applicable and to the extent that this is possible, and performed by two independent investigators.

All statistical analyses will be performed with SAS. Descriptive statistics will be calculated for all data. Prior to all analyses, we will examine the distributions of continuous variables for departures from normality, separately and in combination, for possible violations of assumptions (e.g., multicollinearity). For continuous variables, the mean and standard deviation will be calculated. Medians and interquartile ranges will be calculated if a continuous variable is skewed. The 95% confidence interval (CI) will be provided as appropriate. Model fit diagnostics will be used to evaluate the appropriateness of linear modeling for primary hypotheses. If appropriate, log transformation may be performed. Statistical significance will be accepted at $p < 0.05$. The analyses will be based on a variety of statistical techniques. Most will focus on the use of multilevel modeling and multilevel structural equation modeling which allows the appropriate analysis of data

that are nested (that is, observations come from the same individual over time).

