Below is a detailed description of all techniques and measurements to be utilized and/or obtained, as well as a complete description of the experimental protocol (see schematic illustration below). First, all participants will complete an in-person screening/familiarization visit (~1.5 hours) to determine eligibility. Thereafter, each participant will complete two 15-day measurement bursts (hereafter referred to as "testing cycles"). Micro-longitudinal measurement burst/testing cycle designs consist of repeated sequences of closely spaced assessments that provide multiple time scales, allowing for the examination of processes unfolding within an individual over short time periods (e.g., days) as well as how these change over longer time intervals (e.g., months). Each 15-day testing cycle consists of 1) an ambulatory assessment of daily stress processes and cognitive function for 14 consecutive days (~2-3 hours in total), 2) daily wrist accelerometry for 14

consecutive days (no additional time burden), 3) daily saliva collection for 4 consecutive days (~1 hour in total), and 4) an experimental visit to assess vascular endothelial function (~6 hours). The two cycles will be separated by ~3-6 months; the lack of standardization of the timing between cycles is purposeful, as it will allow us to begin to more precisely disentangle the temporal patterning of the proposed relations both within- and between-subjects. This protocol is illustrated below:

Pre-Screening: Initial Interview/Survey to Determine Eligibility

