1. Participants are familiarized with the organization, flow, and types of questions in the ambulatory assessments prior to participation. They will practice using the Gorilla experiment builder on their personal mobile device at the screening/familiarization laboratory visit.
2. Participants will complete a morning assessment and an evening assessment each day for 14 consecutive days (Days 1-14). Beginning on the first day of the ambulatory assessments, participants will receive pre-scheduled alert notifications via text/email twice per day (~9a and ~7p), prompting them to complete a short morning survey (2-3 min) and a slightly longer evening survey (5-7 min). These notifications are programmed and generated by Qualtrics or Metricwire and include direct access to the associated survey.
3. The morning survey asks questions about sleep, morning outlook, and anticipatory stress and positive experiences (see attached document “Daily Stress Script”). The investigators do not monitor answers to these surveys on a daily basis; instead, these data are compiled at study completion.
4. The evening survey asks questions about the participant’s daily experiences (stressors, mood, physical symptoms), and memory lapses (see attached document “Daily Stress Script”). The investigators do not monitor answers to these surveys on a daily basis; instead, these data are compiled at study completion.
5. Within both the morning and evening surveys, some questions will ask participants to select a single option, some questions will ask participants to check the boxes of as many options as are relevant to their answer, some questions involve drop down menus, and some questions involve a slider scale.
6. After each survey, participants will complete three brief objective cognitive tasks or “brain games” (see attached document “Daily Cognition Tasks”). The cognitive tasks will be administered using either Gorilla experiment builder (accessed via a link at the end of each Qualtrics survey) or directly within the Metricwire mobile app. If using Qualtrics, participants will click on the link to directly access the tasks in Gorilla experiment builder. This link will include a unique identifier connecting the participant’s survey results to their Gorilla task results. Direction screens are provided before each game.
 - In the *paired associates* task, participants see words paired with numbers and have to recall the number paired with each word.

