- In the *forward number span* task, participants see a series of numbers (from 3-7 digits long) and have to enter the numbers in the order they appeared. In the *backward number span* task, participants again see a series of numbers (from 2-6 digits long) and have to enter the numbers in reverse order.
- In the *spatial n-back* task, participants see 4 squares that change color. When the same square changes color twice in a row, they have to click a button on the screen.

7. During the same 14 days, participants will also wear an accelerometer watch (MotionLogger Actigraph) on their non-dominant wrist during all waking and sleeping hours to objectively assess sleep and activity/sedentary behavior. They will be instructed in its use, including removal of the wristwatch for any water-based activities (e.g., showering, bathing, swimming, etc.).

8. On Day 15 (i.e., the day immediately after completion of the 14-day ambulatory assessments), participants will return to the laboratory for the experimental visit. They will return the accelerometer at this visit.

Daily Saliva Collection (Days 3-6)

1. Participants will be asked to provide saliva samples for 4 consecutive days, beginning on Day 3 of the ambulatory assessments (described above) and continuing until Day 6. These samples will be tested for stress hormones (e.g., cortisol) and indices of mitochondrial function (e.g., cell-free mitochondrial DNA). The home saliva collection kit contains collection instructions (see attached document "Saliva Collection Instructions"), all collection materials, and a saliva collection worksheet (see attached document "Saliva Collection Worksheet") and is provided in a small portable cooler for ease of transportation and storage. All samples are coded and do not contain personal identifiable information.
2. Participants will collect their saliva 4 times per day (once upon awakening and before getting out of bed, once 30 minutes after getting out of bed, once at lunchtime, and once in the evening). Participants will record the date and time of each collected saliva sample. They will collect a total of 16 saliva samples over the 4-day sampling timeframe.
3. To collect saliva, participants will use a salivette, which includes a cotton swab that they will put in their mouth for 2 minutes. After 2 minutes, they will place the cotton swab back in the salivette tube.

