 - Then we insert a thin needle into the skin at each entry mark. The needle's tip travels between the layers of skin for ~2.5 cm (1 inch) and exits the skin at the matching exit-mark.
 - We thread the microdialysis tubing through the needle and then withdraw the needle leaving the tubing in the skin.
 - We prepare up to 3 microdialysis sites.
 - Any hyperemia related to the insertion subsides in about 60 minutes. During this time lactated Ringers or a site-specific pharmacological agent listed below perfuses the microdialysis tubing:
 - lactated Ringers
 - lactated Ringers + mitoTempol
 - lactated Ringers + Tempol
- We use laser Doppler flowmetry to measure cutaneous microvascular blood flow:
 - We tape thin fiber optic laser Doppler flowmeter probes and their holders on the forearm over each microdialysis site.
 - The thin probe measures skin blood flow with a weak laser light. We measure skin blood flow continuously throughout the experiment.
 - We can control the temperature of the holders.
- At the start of the experiment, we obtain ~20 minutes of baseline measurements. During this time, the temperature holders are set to thermoneutrality (33°C/91.4°F).
- Then, we increase the temperature of the holders to 42°C/107°F (0.1°C/sec).
- After skin blood flow stabilizes (~45 min), we switch the fluid in all probes to L-NAME.
- After skin blood flow stabilizes a second time (~45 min), we switch the fluid in all probes to sodium nitroprusside. At the same time, we warm the probe's holder to 43°C (108°F) for ~30 minutes to cause maximal dilation.
 - If a participant is asked to repeat this procedure, it will occur during a separate laboratory visit.

13. At the conclusion of the experiment, we remove the microdialysis tubing from the skin and place sterile bandages over the site. If the subject desires, we place a bag of ice on the site for 10 min to reduce bruising that may occur. The investigators complete an assessment of each microdialysis site and complete the Microdialysis Discharge Form.

14. We measure blood pressure and heart rate before the subject leaves the laboratory.

Subject Participation: A subject may decide not to participate in a particular experimental measurement or procedure or may decide not to participate in the second testing cycle; therefore, in these situations, this portion of the protocol will not be completed. However, all other measurements and procedures will be performed. This will not affect the scientific value of the

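### Does naming only the individual as nesting unit mean that cycle-level effects will get standard errors that are too small?

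*Combined protocol and SAP*

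**What the plan says.** The analysis plan is the answer on analysis and reporting in section 10 (Data). It announces that "The analyses will be based on a variety of statistical techniques", then says most analyses will use multilevel modelling and multilevel structural equation modelling, with significance at p < 0.05. The only remark on structure is that the data are "nested (that is, observations come from the same individual over time". No model equation, number of levels, random effect or covariance structure is given.

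Section 6 (Procedures) describes the design more fully. Each participant has two testing cycles, presented as "repeated sequences of closely spaced assessments that provide multiple time scales". They are meant to show processes over days "as well as how these change over longer time intervals (e.g., months". The cycles are about 3-6 months apart, and "the lack of standardization of the timing between cycles is purposeful".

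Within a cycle, surveys run morning and evening for 14 days. "After each survey, participants will complete three brief objective cognitive tasks", which makes 2 x 14 = 28 cognitive sessions per cycle. For saliva, "They will collect a total of 16 saliva samples over the 4-day sampling timeframe". Blood sampling, endothelial cell collection and the vascular tests belong to the Day 15 visit of each cycle; flow-mediated dilation and pulse wave measures may instead be done at the screening visit. Under Subject Participation, a person "may decide not to participate in the second testing cycle".

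**The concern.** The data have at least three levels: records or days, within cycles, within people. The one sentence on nesting names only the person. Records from the same cycle may resemble each other more than records from the same person months apart. A model with only a person intercept treats all the within-person scatter as independent from record to record.

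Terms that vary only between cycles would then look more precise than they are. These are cycle itself, cycle by gap length, and a once-per-cycle blood or vascular measure used to predict a daily outcome. Change over months is a stated purpose of the two-cycle design, and Aim 3 relates vascular and redox measures to daily cognition, so such terms are plausible.

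A similar point applies to slopes. If the effect of daily stress differs between people and no random slope is fitted, a group-by-stress test on daily records also rejects too often. A reader of section 10 cannot tell which model will be run.

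**Working it through.** The documents give no variance components, power calculation or model, so there is no stated figure to reproduce. The check asks how large the error would be under the least favourable reading.

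**Inputs from the documents.** Two cycles per person. Records per cycle, m: 14 for evening mood, 28 for cognition, 16 for saliva samples (4 if reduced to one value per saliva day), 1 for a measure taken once per cycle. 60 healthy and 60 unmedicated depressed adults, 120 in all. Alpha 0.05, taken as two-sided.

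**Assumptions.** Total variance 1; person variance 0.40; cycle-within-person variance c = 0, 0.02, 0.05 or 0.10; residual variance e = 0.60 - c. Balanced data.

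**Formula.** For the cycle contrast, the true standard error divided by the one from a person-intercept-only model is

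ratio = sqrt[(e + m c) / (e + c m/(2m - 1))],

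and actual type I error = 2 x [1 - Phi(1.96 / ratio)].

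Example, m = 14 and c = 0.05: e = 0.55. Numerator 0.55 + 0.70 = 1.25. Denominator 0.55 + 0.70/27 = 0.576. Ratio = sqrt(1.25/0.576) = 1.47. Type I error = 2 x [1 - Phi(1.33)] = 18%.

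| m | c = 0 | c = 0.02 | c = 0.05 | c = 0.10 |
|---|---|---|---|---|
| 1 | 5% | 5% | 5% | 5% |
| 4 | 5% | 6% | 9% | 12% |
| 14 | 5% | 10% | 18% | 29% |
| 16 | 5% | 11% | 20% | 32% |
| 28 | 5% | 16% | 29% | 42% |

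At m = 14 the ratios are 1.00, 1.21, 1.47 and 1.86; at m = 28 they are 1.00, 1.39, 1.84 and 2.45.

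**Simulation.** Fitted mixed models for 120 people (2,000 runs) agree. At m = 14 and c = 0.05 a person intercept alone gave 18.5% for cycle, 17.6% for cycle by gap and 19.3% for a once-per-cycle predictor. Adding a cycle-within-person intercept gave 4.0-6.5% in every setting. The group main effect stayed at 4.8-5.3% with or without it.

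**Slopes.** With m = 14, c = 0.05, random intercepts only and an assumed between-person slope variance of 0.02 or 0.05 per SD of stress, group by stress on daily records rejected 15.5% or 26.8%. With random slopes by person and by cycle, rates were 4.3-5.8%.

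**Scale of the cycle share.** If the share is expressed against within-person variance instead of total variance, c = 0.02, 0.05 and 0.10 become 0.02/0.60 = 3.3%, 0.05/0.60 = 8.3% and 0.10/0.60 = 16.7%. The type I errors are the same, so a given percentage looks milder on that scale.

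**Which aims are reached.** Aim 1 concerns cytokines and mitochondrial redox balance, and Aim 2 endothelial function. In blood and vascular form these have one visit per cycle, the m = 1 row. (Microdialysis uses up to three skin sites per visit. Treated as three records per cycle, the formula gives 6%, 7% and 10%.) The larger rows apply to mood, which no aim names as an outcome; to cognition, under the exploratory Aim 3; and to saliva, whose mitochondrial DNA may bear on Aim 1.

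**The case for a change.** The strongest case for a change is that the term multilevel modelling covers both the sound and the unsound specification, and that the one explanatory phrase describes the two-level version. This is the only analysis plan supplied, and it sets a 5% threshold without fixing the model on which that threshold depends. One sentence of analysis wording would settle it, with no effect on visits.

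Part of this stands. The structure is unstated, the arithmetic is right, and the exposure is not zero: Aim 3 cognition and the salivary markers are repeated within cycles, and a group-by-stress test on them would need a random slope if slopes vary.

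The rest does not carry. The phrase about the individual explains the word nested in plain terms on an ethics-board form and does not list model levels. The study-benefits text in section 8 does not strengthen the slope argument either. There, responsiveness to stress is what predicts inflammation, redox balance and vascular function. A group-by-stress test on daily mood asks something else, namely whether responsiveness differs between groups.

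The flexible gap between cycles is a separate matter. Each person has a single gap value, so any gap effect is a non-randomised comparison between people. The plan states no gap hypothesis that this would undermine, and change within a person remains estimable.

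**Conclusion.** The concern does not call for a change. Section 10 leaves the random-effects structure open but commits to the class of methods that handles it. Section 6 sets out the two time scales and says the relations will be examined within and between people. Analysts fitting multilevel models to two bursts of daily records can be expected to include a cycle level, and random stress slopes where those are tested.

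The inflation of 10-29% at 14 records per cycle, or 16-42% at 28, needs two conditions: a person-intercept-only model, which the plan never states, and cycle variance of 2-10% of the total, which is assumed. At zero cycle variance there is no inflation, and with a cycle intercept the rate is about 5%. The figures also assume balanced data; missed surveys and skipped second cycles would alter them but not their direction.

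Group main effects and outcomes with one value per cycle are unaffected in this way, so Aims 1 and 2 lie mostly outside the problem. What remains is ordinary under-specification, bearing mainly on exploratory cognition and salivary markers. It is not a demonstrated error.
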